## **Study protocol**

*The conventional group* received washing oneself and dressing training from the same OT in the occupational therapy unit for 3 days. On the 4th day of training, the OT supervised the patients while performing these tasks in the rehabilitation ward. After that, a nursing staff took responsibility for these activities in a traditional way of nursing care until day 14. Duration of training session was one hour per day.

*The experimental group* received the new “seamless self-care training” technique, which was characterized by a collaboration between OTs and nurses. The training team consisted of two OTs with standardized training skills according to the self-care checklist for dressing and washing oneself (see appendix). The patients received training in the occupational therapy unit for 2 days and then were supervised by OTs at the rehabilitation ward for the next 2 days. On the 4th day of the training, one nursing staff came along with the OT in order to learn how to facilitate the patients according to their abilities to carry out these tasks. After that, the patients received further training from the nursing staff until day 14. Duration of training session was one hour per day. In this group, the nursing staff guided the patients to perform dressing and washing oneself according to the self-care checklist for dressing and washing oneself.

In both groups, each patient was in contact with and trained by only one OT and one nurse throughout the period of the study.

In order to reduce cross-contamination of the training techniques, each technique was delivered in separate periods of time. We first finished collecting data in the conventional group for one month and then conduct the seamless self-care training technique with the experimental group. During the study, patients received physical therapy or other treatments that did not affect dressing and washing oneself abilities.

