### *Outcome measurement*

For the main outcome, patients' abilities in dressing and washing oneself were evaluated by another OT on day 1 and day 14 of the program in both groups. However, since there were no specific detailed measurements for assessing such abilities after a stroke, the authors developed steps of dressing and washing oneself, so called “Self-care checklist for dressing and washing oneself”. Based on task analysis, these two self-care activities consisted of 5 sequential activities: taking off a shirt, taking off pants, washing oneself, putting on a shirt and putting on pants. Each activity was composed of 4 steps, so there were 20 steps in total. Each step could be scored as 0, 1, or 2. A score of 2 meant the patients could perform the task independently, while 1 meant the patients could do the task with verbal cueing, and 0 meant the patients could not perform the task within 5 minutes or needed assistance to complete the task. Therefore, the maximum score was 40 for the independent performance measurements of dressing and washing oneself. This checklist had a high correlation with the Modified Barthel Index as analyzed with Spearman's correlation  $r = 0.764$ ,  $p < 0.001$ .

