## **Statistical analysis plan**

Demographic and clinical variables were summarized using descriptive statistics. Continuous variables were described as mean with standard deviation (SD) and median with an interquartile range (IQR). Categorical variables were described by frequency and percentage. Statistical data analysis was performed using SPSS, Version 18.0, and a p-value of 0.05 was considered to be statistically significant. The differences in the outcome of self-care training and self-efficacy

between the two groups were analyzed by independent t-test, or within group by paired t-test, while differences between groups covariate by day 1 were analyzed by analysis of covariance (ANCOVA). The gain level was analyzed by chi-square test for assessing trends.

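### Gain level is compared by a trend test with no day-1 adjustment between groups treated in successive periods; on a checklist capped at 40, a day-1 difference can create or hide a trend

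*Combined protocol and SAP*

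**What the plan says.** The Statistical analysis plan section lists three kinds of between-group comparison.

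- An independent t-test, with no covariate mentioned.
- ANCOVA, "while differences between groups covariate by day 1 were analyzed by analysis of covariance (ANCOVA".
- For gain level, one sentence: "The gain level was analyzed by chi-square test for assessing trends".

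The last sentence names no covariate, stratification or cut-points. It does not say whether gain is absolute or relative, or whether it concerns the checklist or self-efficacy, both of which are named just before it. The significance threshold is given as "a p-value of 0.05 was considered to be statistically significant".

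The Outcome measurement section builds the checklist from five activities: "Each activity was composed of 4 steps, so there were 20 steps in total", and "Each step could be scored as 0, 1, or 2". It concludes that "the maximum score was 40 for the independent performance measurements of dressing and washing oneself". Patients "were evaluated by another OT on day 1 and day 14 of the program in both groups".

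The Study protocol section describes how the groups were formed: "We first finished collecting data in the conventional group for one month and then conduct the seamless self-care training technique with the experimental group". The text available describes no randomisation, matching or stratification.

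**The concern.** A gain on a capped scale depends on where the patient starts. Someone who enters at 34 can gain at most 6 points, and someone who enters at 15 can gain up to 25. If one group happens to start higher, fewer of its patients have room to reach the upper gain levels, even when care and recovery are identical. Recruiting the groups in successive periods leaves such a difference to chance and to any change in the patients admitted. The plan treats the day-1 score as worth adjusting for in one analysis and then leaves it out of this one.

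At stake is the interpretation of the gain-level result. A trend could be credited to the training technique when it reflects starting scores, or a real benefit could be masked if the experimental group started higher.

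**Working it through.** **1. The cap.** From Outcome measurement: 5 activities × 4 steps = 20 steps, and 20 × 2 points = 40. This reproduces the stated maximum. The largest possible gain is therefore 40 − day-1 score: 40 − 34 = 6, and 40 − 15 = 25.

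**2. Inputs that must be assumed.** The documents give no sample size, day-1 mean, SD, expected gain or cut-points. I assumed:

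- gain level is points gained on the checklist, in four levels cut at 5, 10 and 15;
- the uncapped gain is the same in both groups (mean 10, SD 6), so there is no treatment effect;
- day-1 SD is 8, with scores limited to 0 to 40 and rounded to whole points, and each gain is capped at 40 − day-1 score;
- there are 20 or 30 patients per group, and alpha is 0.05, taken as two-sided.

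**3. Test.** Linear-trend chi-square = (N − 1)r², where r is the correlation between group and gain level, referred to chi-square on 1 df.

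**4. Why the starting level matters.** With a top cut of 15, a patient starting above 40 − 15 = 25 cannot reach the top level. Under a normal day-1 score that share is 1 − Φ((25.5 − mean)/8):

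- mean 28: 1 − Φ(−0.31) = 62%; mean 24: 1 − Φ(0.19) = 43%;
- mean 16: 1 − Φ(1.19) = 12%; mean 8: 1 − Φ(2.19) = 1%.

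**5. Rejection rates with no treatment effect.**

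| Day-1 means | 20 per group | 30 per group |
|---|---|---|
| equal | about 5% | about 5% |
| 28 v 24 | 11% | 14% |
| 30 v 22 | 26% | 41% |
| 20 v 16 | 5.5% | 6.6% |
| 14 v 10 | 5.6% | 5.3% |
| 16 v 8 | 5.4% | 5.2% |

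With 3,000 simulated trials in a setting, the simulation error is about √(0.05 × 0.95/3000) = 0.4 percentage points at 5% and √(0.4 × 0.6/3000) = 0.9 at 40%. At 28 v 24, 33% v about 42% of patients gain 10 or more points. At 30 v 22 it is 28% v 46%.

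**6. Sensitivity to the assumed gain.** With an uncapped gain of 12 (SD 6) and 30 per group, a 4-point gap gives 4.6%, 9.8% and 25.0% when the lower-starting group has a mean of 12, 20 and 28. An 8-point gap gives 9.0%, 40.3% and 76.7%.

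**7. Sensitivity to the definition.** If levels are cut at 25%, 50% and 75% of the available headroom instead, rejection at 30 per group is 15% to 16% for a 4-point gap and 41% to 51% for an 8-point gap. A relative definition does not remove the problem.

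**8. Direction.** Suppose low starters recover more slowly (gain rises 0.3 points per day-1 point, day-1 SD 6, gain SD 5, 30 per group). Day-1 means of 8 v 12 give mean gains of 6.6 v 7.6 and 10.8% rejection. Means of 8 v 16 give 6.6 v 8.6 and 32.7%. Here the higher-starting group appears to do better.

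**9. Effect of adjustment.** Under the assumptions in step 2, linear regression of level on group and day-1 score rejects in about 5% to 6% of trials. ANCOVA of day 14 on group and day 1, under the assumptions in steps 6 and 7, rejects in 3.4% to 6.2%. The proportional-odds model rejected in 3% to 5% of 300 runs at 30 per group. Its likelihood-ratio test rejected in 6% to 8.5% of 200 runs at 20 per group. With so few runs the simulation error is about √(0.05 × 0.95/300) = 1.3 and √(0.05 × 0.95/200) = 1.5 points, so the model may be slightly liberal in very small groups.

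**The case against.** The strongest reply is that the harm depends on conditions the documents do not show. The ceiling matters only if many patients start high. These are ward inpatients in daily self-care training, and any step that needs help scores 0, so low starting scores are quite plausible. In that range even an 8-point imbalance is harmless under the step 2 assumptions (16 v 8). This stands, and it rules out saying that the test will give a false result.

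Second, gain level is undefined. If it concerns self-efficacy, the cap of 40 does not apply. This also stands. The comparison would still lack a baseline adjustment, but the figures above would not describe it.

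Third, the plan already has a day-1 ANCOVA for between-group differences, and nothing makes gain level the main result. That confines the harm to one supporting result. It does not make the trend test sound, and the plan does not say which analysis prevails if the two disagree.

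A reader might infer that the trend test is biased towards the experimental group, or that the whole between-group comparison ignores day 1. The documents support neither. No day-1 scores are given, the bias can run either way (step 8), and the ANCOVA is planned alongside the unadjusted t-test.

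**Conclusion.** The concern holds in a conditional form. As written, the gain-level test ignores the day-1 score, and the groups are not protected by design against a day-1 difference. If gain level is points gained on the checklist, such a difference can raise the false-trend rate from 5% to about 11% to 14% (28 v 24) or 26% to 41% (30 v 22) with 20 to 30 per group. When patients start low the rate stays at about 5% to 7%. Apart from the cap of 40, every input to those rates is assumed. The size therefore cannot be fixed from the documents, and neither the presence nor the direction of a bias is established. The weakness touches a supporting result and should be corrected, because the day-1 score that corrects it is already collected.

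**What to change.** - State which outcome gain level refers to, whether gain is absolute or relative, and the cut-points.
- Replace the trend test with an ordinal (proportional-odds) regression of gain level on group, with the day-1 score as covariate. Alternatively, show the gain-level table as description only and take the between-group conclusion from the planned day-1 ANCOVA.
- If gain is measured on the checklist, report for each group how many patients had a day-1 score too high to reach the top gain level.

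The cost is a change of analysis wording. No new data are needed, and ordinal regression is a standard SPSS procedure. The downside of the model is a proportional-odds assumption that must be checked in what may be a small sample; the descriptive option avoids this. Neither route removes other differences between the two calendar periods, and the report should say so.
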